Participants' answers and comments will be written down by the note-taker during the focus groups. Focus groups will not be transcribed. Once both focus groups are completed, these notes will be compiled together in a single Word document, in a list format, without any identifying information - anonymized. Based on participants' reactions and feedback overall, adjustments will be made to the video as it is being developed by the media design company Akufen with whom we are working to develop the video intervention.

Funding

This study is funded by the McGill Interdisciplinary Initiative in Infection and Immunity (MI4) (<https://www.mcgill.ca/mi4/>). Neither the principal investigator nor the institution is in a situation of conflict of interest as a result of this funding.

Risks and Concerns

Participating in this research study has no known physical risks. There is no evidence in the scientific literature that eliciting altruism could produce negative consequences or emotions in participants. However, it is possible that participants of the focus group may experience discomfort or upset as the result of the research intervention (video and discussion about its content). Participants will be informed that they are free to refuse to answer any question or stop their participation.

At the end of each focus group, participants will be asked whether they have questions or concerns. Participants will also be provided with the link to a governmental website where they will find available resources in their regions: <https://www.canada.ca/en/public-health/services/mental-health-services/mental-health-get-help.html>.

Participants will also receive to the contact details of the principal investigator and the study coordinator should they have any additional questions or comments about the study. In addition, they will be provided with the contact numbers for the Local Commissioner of Complaints & Quality of Services at the JGH and for our laboratory.

Participants will also be provided with a list of online resources about the COVID-19 vaccines:

- National Advisory Committee on Immunization (NACI) <https://www.canada.ca/en/public-health/services/immunization/national-advisory-committee-on-immunization-naci/recommendations-use-covid-19-vaccines.html>

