The survey company Dynata uses a survey software called Decipher, and information collected as part of this survey will be stored on a Decipher Canadian server. All information collected will be stored in Canada, on Canadian servers for a duration of three months starting after the data has been collected, to provide the research team with enough to ensure the dataset is complete. Anonymized survey data collected by Dynata will be sent to the Study Coordinator who will be in charge of overseeing the storage of data and study documents. This anonymized survey data will be stored on the “[name] File Share” stored on a secure Lady Davis Institute server, where backups are being performed regularly by the LDI and stored files are encrypted (only accessible by individuals who have the credentials to access the data). These files will be accessible remotely to designated members of the research team through a File Cloud. Five (5) lab members will have access to this data (the Study Coordinator, two Research Associates, a Master’s student and the Principal Investigator). These individuals will enter their LDI account credentials to obtain access to the electronic files stored on the [name] File Share. This data will be stored and kept for 10 years, and then permanently destroyed as per CIUSSS-West-Central Montreal policy. The security tool BC Wipe (www.jetico.com) will be used for permanent destruction of the electronic files.

Incidental Findings

This study does not involve medical sample analysis, therefore this is not applicable here.

Participants will be provided with the research team’s contact information, and if they express concerns or discomfort during the study or afterwards, we will be able to direct them to relevant resources for them to seek help.

Communication and Publication of Research Results

The results of this study will directly inform development of public health strategies to help promote COVID-19 vaccine uptake among younger Canadians in order to control the pandemic in the future and protect those at higher risk of hospitalisation and death (e.g., elderly,

those with chronic diseases). Results will be shared with the Public Health Agency of Canada and the Institut national de santé publique du Québec, whose representatives are co-investigators on this project. Publication of results in the peer-reviewed scientific literature are also planned.

References

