Document Cover Page

Full Analysis Plan

Study Title:

Enhancing COVID-19 Vaccination Intentions by Eliciting Prosocial Altruistic Motives:
Evaluating the Efficacy of a Brief Video-Based Intervention

NCT number: NCT04960228

Date of Document: February 5th, 2022

Analysis Plan

Sociodemographics

For baseline sociodemographics we calculated proportions, means (and standard deviation, SD) and used the Pearson Chi-Squared Test and the Welch two sample t-test to evaluate if the two study groups differed significantly.

Objectives 1 and 2.

At baseline and post-intervention and for each of the study groups we calculated the proportion of participants in each of the four PAPM intention stage i.e., *unengaged*, *undecided*, *decided not*, and *decided to*. For each study group we calculated the pre-to post transitions in intentions to receive the COVID-19 vaccine. To estimate the pre-to-post intervention change in vaccine intentions we used a binary outcome (i.e., Vaccine intenders corresponding to the stage *decided to*; and Vaccine non-intenders that included stages *unengaged*, *undecided*, and *decided not*) and the McNemar's Chi-squared test. Post intervention, we estimated the between group difference in vaccine intentions using the four-stage PAPM outcome and the Pearson Chi-Squared Test.

Exploratory Analyses with PAPM stages

To estimate pre to post changes in PAPM intention stages we conducted exact tests of symmetry (4x4 contingency tables) that comprise pairwise McNemar tests (using the “nominalSymmetryTest” function available in the R package “rcompanion”) (1). For each study group we used the significant transitions between vaccine intention stage pairs for calculating the total number of participants that changed towards increased vaccination intentions (e.g., from *undecided* to *decided to*) and estimated the between-group difference using the Chi-squared two-sample test for equality of proportions.

All statistical analyses were conducted using the R software v. 4.0.5.(2).

References

1. Mangiafico S. Package 'rcompanion' 2022 [Available from: <https://cran.r-project.org/web/packages/rcompanion/rcompanion.pdf>].
2. R Development Core Team. R: A Language and Environment for Statistical Computing. R Foundation for Statistical Computing Vienna, Austria 2005 [Available from: <http://www.R-project.org/>].

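### The SAP's exploratory between-arm test of stage change counts only movement towards vaccination, so it can show a gain for the video when net change is the same in both arms

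*SAP*

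**What the plan says.** The relevant SAP section is headed "Exploratory Analyses with PAPM stages". It proceeds in three steps.

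- Within each arm, pre-to-post change is examined by "exact tests of symmetry (4x4 contingency tables) that comprise pairwise McNemar tests".
- The result acts as a filter: "For each study group we used the significant transitions between vaccine intention stage pairs". Over the pairs that pass, the quantity taken forward is a sum in one direction only, which the SAP describes as "calculating the total number of participants that changed towards increased vaccination intentions".
- The arms are then compared on that count: the SAP "estimated the between-group difference using the Chi-squared two-sample test for equality of proportions".

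No count of movement away, and no net count, is carried into a between-arm comparison. The SAP does not say whether the towards total is gross or net within a selected pair. The wording reads as gross.

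Under Objectives 1 and 2 the SAP plans stage proportions by arm at both time points, per-arm transitions, a within-arm McNemar test of intenders against non-intenders, and a post-intervention Pearson test between arms on all four stages. The binary outcome groups *unengaged*, *undecided* and *decided not* together ("Vaccine non-intenders that included stages").

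**The concern.** A persuasive message can move some people towards vaccination and others away. A between-arm test that adds up only the first group rises with any extra movement, including movement that is fully offset. Movement away is the adverse result most relevant to a vaccination message: *decided to* moving to another stage, or *unengaged* or *undecided* hardening to *decided not*. The data to measure it are collected from every participant.

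The protocol's section on communication of results says: "The results of this study will directly inform development of public health strategies to help promote COVID-19 vaccine uptake among younger Canadians". A gain taken from the towards count alone could enter that use although losses cancel it.

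**Working it through.** **Inputs.** From the protocol (Sample): 1315 per arm, two-sided 5%, 80% power, 40% baseline hesitancy. The SAP gives no expected transition rates, so every rate below is an assumption.

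**The plan's own figures.** The SAP states no figure for this analysis.
- Between arms: (1.96·√(2·0.3735·0.6265) + 0.8416·√(0.40·0.60 + 0.347·0.653))² / 0.053² = 1307 per arm for 40% v 34.7%. The stated 5-6 points at 1315 per arm therefore reproduces.
- Paired: the 1315 pairs do not reproduce. The stated inputs (40% to 35%, correlation 0.45) give 813. That is a separate matter and nothing here depends on it.

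**Worked example, one stage pair (*undecided* and *decided to*), assumed counts.** Video: 92 up, 53 down. Control: 53 up, 13 down.
1. Filter (exact McNemar): 92 v 53 gives p = 0.0015; 53 v 13 gives p = 7×10⁻⁷. Both arms pass.
2. Planned test: 92/1315 = 7.0% v 53/1315 = 4.0%. With continuity correction, χ² = 2630·(|92·1262 − 53·1223| − 1315)² / (145·2485·1315²) = 10.54, p = 0.0012, favouring the video.
3. Movement away, by the same formula: 53/1315 = 4.0% v 13/1315 = 1.0%, χ² = 23.64, p ≈ 10⁻⁶. No such test is planned.
4. Net change: video (92 − 53)/1315 = 2.97%; control (53 − 13)/1315 = 3.04%. The difference is −0.08 points. Each arm's variance is [(up + down)/n − net²]/n, so the SE is √(0.0000832 + 0.0000375) = 0.0110 and the 95% CI is −2.2 to +2.1 points.

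**Simulation of the full SAP rule.** Per-arm exact filter at 0.05, gross towards count over the pairs that pass, two-sample χ² with continuity correction, 1315 per arm. In rows 2 and 3 the assumed baseline is 8% *unengaged*, 22% *undecided*, 10% *decided not*, 60% *decided to*, with control movement of 1% each way between *undecided* and *decided to*. The true net difference is zero in every row.

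| Assumed scenario | Rule finds the video better |
|---|---|
| 1. One pair, video 7% up/4% down v control 4% up/1% down | about 84% (both arms pass the filter in about 89%) |
| 2. Extra x *undecided* to *decided to* and equal x *decided to* to *decided not*; x = 2, 3, 4, 5% | 94.7, 99.9, 100, 100% |
| 3. One pair, symmetric: video 5% up/5% down v control 1%/1% | 4.0% (100% without the filter) |

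With Bonferroni-adjusted pairwise tests, row 2 becomes 82.9, 99.1, 99.9 and 100%. With net change as the between-arm measure, rows 2 and 3 give a false benefit in 2.3-2.7% of trials, close to the nominal 2.5%.

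**What the other planned analyses show.**
- Binary McNemar, video arm: in row 2 it rejects in 3-5% of trials, so it correctly shows no net change in intenders. In the worked example it gives p = 0.0015, a true within-arm rise that control shares. It cannot register *undecided* moving to *decided not*, since both are non-intenders.
- Four-stage Pearson: in the worked example on the assumed baseline, the post-intervention counts are 105/250/132/828 v 105/249/132/829, p > 0.99. In row 2 it rejects in 34, 66, 90 and 99% of trials although the share of intenders is unchanged, because *decided not* has grown.

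**The case against.** The strongest reply is that the plan as a whole is not one-directional. The analysis in question is labelled exploratory. The four-stage Pearson test compares randomised arms after the intervention and so reflects net movement; in the worked example it is flatly null. *Decided not* is its own category there, so hardening can register: moving 53 v 13 people from *undecided* to *decided not* on the assumed baseline gives p = 0.047. Stage proportions and transitions are reported by arm in both directions. The filter also removes most symmetric backfire within one pair. All of this stands, and it limits the point.

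It does not remove it. The Pearson test has no direction, so a significant result caused by growth in *decided not* could be read as support for the towards count. The per-arm transitions are descriptive, and the McNemar test is within-arm.

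Three stronger readings are tempting, and the documents do not support them.
- *The plan hides backfire or never compares it between arms.* The per-arm transitions and the four-stage test contradict this. What is missing is a directional between-arm estimate of movement away and of net change.
- *A pair with significant downward imbalance adds its upward minority to the benefit count* (for example 20 up v 50 down, exact p = 0.0004). This requires a gross count and admission of downward pairs. The SAP states neither, and its text can also be read as excluding such a pair.
- *The protocol rules out backfire.* Its sentence "There is no evidence in the scientific literature that eliciting altruism could produce negative consequences or emotions in participants" stands in the risk sections and concerns participant discomfort, not movement in vaccine intention.

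**Conclusion.** The point holds as a limited one. The SAP's only between-arm comparison of individual change is towards-only, and it can show a gain for the video at equal net change. The size depends on how losses arise: about 84% of trials in the asymmetric one-pair case, about 95-100% when losses run through a different pair, and about 4% when gains and losses are symmetric within a pair. These figures rest on assumed stage mix and transition rates, gross counting within selected pairs, and 1315 per arm. They show what the rule can do, not how likely backfire is. The consequence is confined to an exploratory claim, but that claim is easily corrected and the results are intended for public health use.

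**What to change.** In the same SAP paragraph, classify every participant in both arms from a pre-stated table covering all 12 off-diagonal transitions:

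- **Towards (5):** any other stage to *decided to* (3); *decided not* to *undecided* or *unengaged* (2).
- **Away (5):** *decided to* to any other stage (3); *unengaged* or *undecided* to *decided not* (2).
- **Assigned in advance (2):** moves between *unengaged* and *undecided*, for example as neutral.

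Apply the table without the per-arm significance filter. The filter is a hazard in itself: with identical transitions in both arms (3% towards, 2% away), the SAP rule declared the video better in 21.5% of simulated trials, against a nominal 2.5%.

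Report the between-arm difference with 95% CI for towards, away and net (towards minus away). Base any exploratory claim of increased intention on the net difference, not on the towards count alone. Net gives each move equal weight, so it should be read beside its two components.

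The cost is SAP wording and a few lines of R on data already collected. The SAP is written in the past tense, but the existing dataset can still be analysed this way. The downside is two more exploratory estimates to report.

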Document Cover Page

Study Protocol

Study Title:

Enhancing COVID-19 Vaccination Intentions by Eliciting Prosocial Altruistic Motives:
Evaluating the Efficacy of a Brief Video-Based Intervention

NCT number: NCT04960228

Date of Document: May 7th, 2021

RESEARCH STUDY TITLE: Enhancing COVID-19 Vaccination Intentions by Eliciting Prosocial Altruistic Motives: Evaluating the Efficacy of a Brief Video-Based Intervention

PRINCIPAL INVESTIGATOR: Dr, [name], Lady Davis Institute for Medical Research, [name] [contact] ([name]) Email: [contact]

CO-INVESTIGATORS AND/OR RESEARCH ASSOCIATES/ASSISTANTS:

Collaborators: [name] (Indiana University School of Medicine), [name] (NACI), [name] (INSPQ)

Research Associates: [name], [name]

Research Assistant: [name], [name]

SOURCE OF FUNDING: This project is supported by the McGill Interdisciplinary Initiative in Infection and Immunity (MI4)

Introduction

The COVID-19 vaccine is the most effective way to arrest the pandemic. A high vaccine acceptance rate is needed to achieve community immunity; however, current COVID-19 vaccine acceptance rate remains low, particularly among younger Canadians. We were recently awarded a McGill MI4 grant to examine the efficacy of a video intervention eliciting altruism on increasing younger Canadians' (ages 20-39) intentions to receive the COVID-19 vaccine.

Literature Review

As Canada's COVID-19 cases of infection and deaths continue to increase, it is imperative to stop the spread of the virus. Younger people (between ages 20-39) are more likely to spread the virus (1), while experiencing milder symptoms than older individuals. The COVID-19 vaccine is the most effective way to control the pandemic by achieving community immunity through high vaccination rates. However, around 40% of Canadians are hesitant to accept the vaccine (2). In particular, younger age has been associated with COVID-19 hesitancy (3). Previous studies have found that individuals who demonstrated more prosocial behaviours were more likely to get a vaccine if it benefits others whom they value (4-7). Only two studies examined the usage of a text-based altruistic intervention to increase vaccine uptake (8, 9), but they were not specific to the Canadian context. In addition, video-based messaging is known to have high appeal to younger audiences, as seen by the success of platforms such as TikTok and Instagram.

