While we have essentially kept the pre-post evaluation format as per the approved MI4 proposal we have decided to improve the research design by adding a control condition, therefore making this a randomized controlled trial. The full research proposal that has been submitted to the McGill Interdisciplinary Initiative in Infection and Immunity (MI4) and approved for funding is attached in section 13 "Other document" on Nagano (F11P-20611).

Methods

Sample

A survey will be administered online to a sample of Canadian residents aged 20-39 years old in both English and French. Our only exclusion criterion is having received any number of doses of any currently available COVID-19 vaccine. A sample of 2,630 participants will be drawn from a database panel provided by Dynata, the world's largest first-party data and insight

platform, to complete the survey. Dynata's use of Canadian census data from Statistics Canada and quota-based sampling will ensure that the sample will closely match the Canadian population in terms of sex, first language English/French, population density (i.e. urban vs. rural), and household income.

To calculate the required sample size for the within-participant change in vaccine hesitancy (i.e., pre-post intervention) we used the latest survey data showing that approximately 40% of Canadians in this age group are COVID-19 vaccine hesitant i.e., don't know yet or would refuse vaccination. Estimating a 5% decrease of hesitancy in the intervention group and a correlation of about 0.45 between paired observations, the intervention group requires a sample size of 1315 pairs for detecting a 5% change of marginal proportions at a power of 80% and two-sided significance of 5%.

We will use 1:1 randomization of participants. Thus, 50% will be allocated to the intervention and 50% to the control group. Using equal size groups will allow us to detect a between group difference in vaccine intentions of 5-6% with a power of 0.8 and a two-sided significance of 5%. The total sample required for this study is 2630 participants i.e., 1315 in the intervention group and 1315 in the control group.

Recruitment Strategy

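### The SAP tests the randomized contrast with a four-stage test that is not documented in advance and that falls short of the protocol's detectable-difference statement

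*SAP*

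**What the plan says.** **Protocol** (cover page: "Date of Document: May 7th, 2021"). The trial part has no statistical analysis section; the only analysis section, Analytic Process, concerns the focus-group notes. What is fixed for the trial stands in the second Methods section, under Sample:

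- A paired contrast in the video arm. The inputs are that "approximately 40% of Canadians in this age group are COVID-19 vaccine hesitant" and "Estimating a 5% decrease of hesitancy in the intervention group and a correlation of about 0.45 between paired observations". The text derives 1315 pairs from these, "at a power of 80% and two-sided significance of 5" per cent.
- A between-group contrast. With 1315 per arm the trial is said to "detect a between group difference in vaccine intentions of 5-6% with a power of 0.8 and a two-sided significance of 5" per cent.

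Procedure fixes the instrument: the four PAPM stages, asked before and after the video or text. No passage says which contrast is primary, which test is used, or whether the between-group outcome is binary or four-stage.

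**SAP** (cover page: "Date of Document: February 5th, 2022"). It is written in the past tense throughout and closes with "All statistical analyses were conducted using the R software v. 4.0.5". Under Objectives 1 and 2 it defines a binary outcome (the stage of having decided to be vaccinated against the other three) and applies McNemar's test to it within arms. For the randomized comparison it drops that binary outcome: "we estimated the between group difference in vaccine intentions using the four-stage PAPM outcome and the Pearson Chi-Squared Test". The symmetry tests and the comparison of participants who moved towards vaccination are under a heading that marks them exploratory. The SAP cites no earlier version and gives no sign-off or data-access date.

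**The concern.** The between-group comparison is the only one that randomization protects. For it, the document that carries an earlier date fixes neither the test nor the form of the outcome. The document that does fix them reads as a record of finished work. A reader therefore cannot tell whether the four-stage test was the intended analysis or one of two that were open once the data were in hand.

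Two things are at stake. First, if the choice was open, a nominal 5% result does not carry a 5% error rate. Second, the four-stage test does not answer the question that the protocol's detectable difference describes. It spreads its power over three degrees of freedom, and it responds to any rearrangement of stages, including one that leaves the number of intenders unchanged. The protocol says public health authorities will use the results, so the main comparison should show directly whether intention rose and by how much.

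**Working it through.** **Inputs.** From the protocol's sample-size text: n = 1315 per arm (taken as given), 40% hesitant, two-sided 5%, differences of 5 to 6 points. Assumption: the control arm stays at 40% non-intenders after the intervention.

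**1. Reproduce the protocol's between-group statement.** For two proportions p₁ = 0.40 and p₂ = 0.40 − d, with mean p̄:

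power = Φ{[d√n − 1.96√(2p̄(1−p̄))] / √(p₁(1−p₁) + p₂(1−p₂))}

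At d = 0.053: p̄ = 0.3735, 2p̄(1−p̄) = 0.4680, so Φ[(0.053 × 36.263 − 1.96 × 0.6841)/0.6831] = Φ(0.851) = 0.803. The protocol's 5-6 points at 80% power is therefore what a two-proportion test gives.

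**2. Same data, four-stage test.** Assume that the three non-intender stages shrink in proportion. The noncentrality of the 2×4 Pearson statistic then equals that of the 2×2 table, whatever the stage shares:

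λ = n d² / [2p̄(1−p̄)]

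The critical value rises from 3.841 (1 df) to 7.815 (3 df).

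| Difference | λ | Two-proportion power | Four-stage power |
|---|---|---|---|
| 5 points | 1315 × 0.0025/0.46875 = 7.01 | 75.5% | 59.1% |
| 5.3 points | 1315 × 0.002809/0.4680 = 7.89 | 80.3% | 64.8% |
| 6 points | 1315 × 0.0036/0.4662 = 10.15 | 89.0% | 76.8% |

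Under this assumption the four-stage test does not reach 80% anywhere in the stated 5-6 point range.

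**3. Significance without any change in intenders.** Take illustrative control shares of 5% unengaged, 20% undecided, 15% decided against and 60% decided for. Let the video arm move 5 points from undecided to decided against, with intenders at 60% in both arms. Each of the two cells that move has mean 0.175 and deviates by 0.025 in each arm, so λ = 1315 × 4 × 0.025²/0.175 = 18.8, and the four-stage test is significant about 97% of the time. The binary contrast is zero. The shares and the shift are assumptions; the example shows only what the test can respond to.

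**4. Error rate if either between-group test could be reported.** With no effect, the 3-df statistic splits, in large samples, into the 1-df binary part A and an independent 2-df part B. Either test is significant if A > 3.841 or A + B > 7.815. Hence:

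P = 0.05 + e^(−7.815/2) × 2√3.841/√(2π) = 0.05 + 0.0201 × 1.564 = 0.081

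This does not depend on the stage shares. Simulation with 1315 per arm agrees: about 0.05 for each test alone and about 0.08 for either.

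**The case against.** The strongest reply is that the protocol fixes more than it seems to. It gives two contrasts and a two-sided 5% level, and sizing on a paired change in marginal proportions in effect implies a McNemar-type test in the video arm. It also specifies the same four stages that the SAP uses. That stands. It would be wrong to say that the protocol leaves the outcome analysis wholly open; the gap is the form of the between-group outcome and its test.

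A reader might infer from the dates and the past tense that the four-stage test was picked because of its result. The documents do not support that. They give no dates for recruitment or data receipt, and past tense shows when the text was written, not when the choice was made. The protocol's Study design section also cites a full funding proposal, not provided here, that could contain a plan. The same section says the control condition was added to that proposal's pre-post format, so a between-arm test in it is unlikely but not excluded. Moving to the less powerful of two tests is also weak evidence of a search for significance.

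A reader might also count the McNemar and upward-mover tests as further open choices and arrive at a larger error rate. That does not hold: the first matches the contrast that the protocol sized, and the second is already labelled exploratory.

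Finally, the protocol derives 1315 from the paired contrast and does not rank the between-group one above it. It also does not call the between-group outcome binary; that is inferred from a difference expressed in percent and from the power reproducing. So naming the binary contrast as main is a judgement made now, not a return to a documented primary analysis.

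**Conclusion.** The point holds in a limited form. Pre-specification of the between-group test is undocumented; it is not shown to have been absent. The four-stage test loses about 16 percentage points of power at 5 and 5.3 points and 12 at 6, relative to the test that reproduces the protocol's own statement. These losses assume 40% non-intenders in the control arm and proportional shrinkage of their stages; a different pattern of movement would change them, and could favour the four-stage test. That the test can be significant with intenders unchanged follows from its form and does not depend on those assumptions.

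The type I error is about 8% if either between-group test could have been reported, and 5% if the four-stage test was in fact fixed beforehand. A dated plan that precedes data access would settle which applies. It would not remove the mismatch with the stated detectable difference.

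**What to change.** In the SAP and in all reports:

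1. Make the between-group difference in the post-intervention proportion of intenders, using the SAP's own binary definition, the main between-group analysis. Report it with a 95% confidence interval and a two-sided 5% test. Give as the reason that it matches the protocol's detectable-difference statement and answers the efficacy question directly.
2. Report the four-stage Pearson test as secondary and not documented in advance.
3. Keep the symmetry tests and the upward-mover comparison exploratory, as they are now labelled.
4. State when the analysis document was written, when the data were received and when the arms were first compared. Call no result pre-specified unless an earlier dated plan is produced.

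The cost is one two-proportion analysis on data already collected and some rewording. The four-stage result loses any confirmatory standing.
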